# 9. Data Security and Confidentiality

All identifiable information about participants, their medical conditions, and other study data will be secured by Evidation Health in accordance with all applicable local and state laws, regulations, and IRB policies regarding collection and distribution of participant information.

Data will be transmitted using secure encrypted protocols and stored on encrypted disks on secure and hardened servers. Administrative access to these servers is limited to only the necessary IT staff at Evidation Health. Survey data may be stored for a minimum of 3 years, consistent with contract and applicable law.

Personally Identifiable Information (PII) is only accessible to a restricted set of individuals, and is only used to distribute study material and for participant support purposes. PII will not be disclosed unless required by regulatory agencies or the IRB in instances consistent with applicable law. Limited Achievement clinical, research and technical team members at Evidation Health only have access to Coded Study Data where all PII is replaced with random unique identifiers. Coded Study Data may also be transferred to external research partners, including Sanofi Pasteur, in accordance with IRB approved uses.

#### 10. Risks and Benefits

Version 1 19 of 22

### 10.1. Potential Risks Associated with the Study

This is a minimal risk study that does not involve any risk beyond what a person would experience in their daily life. While we strive to protect the privacy of personal information and implement appropriate safeguards, complete security cannot be guaranteed. There is the potential risk of loss of privacy associated with this study if another person sees the participant's survey responses on their phone or computer screen. Participants may decline to answer certain survey questions.

### 10.2. Potential Benefits Associated with the Study

Participants of this study will likely not receive any direct benefit from the proposed research; however, society and investigators will benefit from the knowledge gained. This information may contribute to public health and scientific efforts related to vaccination and the prevention of disease for people with cardiovascular disorders. This information may help researchers develop further interventions to increase influenza vaccination.

#### 10.3. Adverse Events

Adverse events will not be actively collected because no pharmaceutical product or medical treatment will be provided or evaluated in this study. Spontaneously reported adverse events received by Evidation Health will be recorded per Evidation Health's Standard Operating Procedures.

Any pharmacovigilance data pertaining to a Sanofi product potentially collected will be notified by Evidation Health to Sanofi Pasteur Pharmacovigilance, who is working with Evidation on this research project, through email ([contact]), within 1 (one) working day for serious adverse events.

A "serious adverse event (SAE)" is defined as any untoward medical occurrence that at any dose:

- Results in death,
- Is life threatening, (Note: the term "life-threatening" refers to an event/reaction in which the patient was at risk of death at the time of the event/reaction; it does not refer to an event/ reaction which hypothetically might have caused death if it were more severe),
- Requires inpatient hospitalization or results in prolongation of existing hospitalization,
- Results in persistent or significant disability/incapacity,
- Is a congenital anomaly/birth defect, or
- Is a medically important event or reaction. Medical and scientific judgment should be exercised in deciding whether other situations should be considered serious, such as important medical events that might not be immediately life-threatening or result in death or hospitalization, but might jeopardize the patient or might require intervention to prevent one of the other outcomes listed in the definition above.

Version 1 20 of 22

# **Appendix**

Please see attached appendix for examples of the intervention messages.

1 OVERVIEW AND INTRODUCTION

Influenza impacts approximately 5-20% of the population of the United States annually, resulting in significant economic impact and public health burden (Molinari et al., 2007). For people with cardiovascular conditions, influenza can be particularly burdensome, thus they are considered a high-risk group (CDC, 2019). Vaccination for influenza remains the most effective primary prevention method against influenza, with effectiveness ranging from 38-48% in the past few years (Centers for Disease Control and Prevention (CDC), 2018; Dos Santos, Tahrat, & Bekkat-Berkani, 2018; Doyle, 2019; Jackson et al., 2017; Rolfes et al., 2019). The CDC reports that the vaccination rate in the 2018-2019 season was 47.9% for individuals 18-64 years of age who have high risk conditions such as cardiovascular conditions (CDC, 2019). While this is higher than the rate of 36.4% in same age individuals without high risk conditions, it is far below the 70% national vaccination rate goal (Healthy People 2020, 2019). Given the increased burden that influenza represents for people with high risk conditions, even small improvements in vaccination rates could result in significant impact and provide benefit to patients, healthcare providers, and insurance payors (Molinari et al., 2007).

To date, there are no large-scale RCTs on digital interventions for increasing vaccination rates in people with cardiovascular conditions. One observational study has demonstrated the potential effectiveness of general messaging and incentives via a health-related app to increase vaccine uptake in the general Canadian population (Dale, White, Mitchell, & Faulkner, 2019), suggesting this kind of intervention could be effective with people with cardiovascular conditions. In a separate study, a large randomized controlled trial (RCT) using digital messaging with incentives to vaccinate was found to be effective in increasing vaccination rates in a general population of adults in the United States (Lee et al., 2020). Of particular interest is a digital RCT in a sample of individuals with diabetes, a population with increased risk of influenza-related complications, that used digital messaging and was found to be effective in increasing vaccination rates (Samson, et al., 2020). An additional study of individuals with diabetes that was a collaboration between Sanofi Pasteur and Evidation also demonstrated the impact of influenza and related complications on data retrieved from wearables; showing that people who developed influenza engaged in less activity around the time of diagnosis and recorded an increased heart rate, a unique passive marker of infection (Samson et al., 2019). These studies all suggest that the development of a digital intervention targeted to individuals with cardiovascular conditions could be beneficial in increasing vaccination rates.

The digital intervention messages were developed using a 3-part approach: 1) a quantitative assessment of more than 800 patient perspectives for people with cardiovascular disorders, assessing their behaviors, thoughts, and beliefs surrounding vaccination; 2) semi-structured interviews with approximately 25 patients who had cardiovascular diseases to gather their perspectives and feedback on proposed intervention messages; and 3) an expert panel of cardiologists, behavioral scientists, and vaccine policy experts for expert input on content and accuracy of scientific information provided. This approach to intervention development was consistent with the Patient Centered Outcomes Research Institute (PCORI) recommendation for developing interventions that increase participant recruitment and retention, improve patient outcomes, and increase research validity and relevance to the real world (Frank, Basch, & Selby, 2014). The intervention messages provide informational content on the influenza vaccine (sourced from the Centers for Disease Control and Prevention and the American Heart Association), specific information about influenza and cardiovascular disorders, and behavioral prompts (e.g., reminders) surrounding influenza vaccination behaviors.

2 STUDY DESIGN

- A 6-month prospective, digital, pragmatic randomized controlled trial to evaluate the effectiveness of an influenza vaccination intervention during influenza season for people with cardiovascular conditions
- Two study arms: cardiovascular disorders digital intervention arm (CVD-I) & cardiovascular disorders without digital intervention arm (control: CVD-C)

3 STUDY OBJECTIVES

3.1 Primary objective

The primary endpoint in this study is to examine differences in self-reported influenza vaccination rates between individuals with cardiovascular disease who receive a targeted digital intervention (CVD-I) aimed at increasing influenza vaccination and those with cardiovascular disease who received no intervention (CVD-C).

3.2 Secondary objectives

The secondary endpoints in this study will examine:

- Predictors of vaccination status, including cardiovascular condition type, vaccine drivers/barriers, and vaccine knowledge, across and between CVD-I and CVD-C.
- Engagement with interventions, including clicking, opening, or completing the intervention messages

3.3 Exploratory objectives

The exploratory endpoints in this study include:

- To describe the self-reported impact of the COVID-19 pandemic on influenza vaccination behavior
- To examine differences in wearable data (i.e., sleep, steps, heart rate) between individuals who
 experience influenza and those who do not, as well as differences in wearable data between
 cardiovascular conditions.

4 SAMPLE SIZE

We determined sample size for a two-arm interventional statistical superiority study design with vaccination rates as the primary outcome of interest (Zhong 2009). Studies on the impact of messaging and reminders to improve influenza vaccination rates show a range of effect sizes from 2.5 - 3.5% (Nehme et al., 2019, Hurley et al., 2018). As noted earlier, CDC reported vaccination rates are 47.9% for adults between the ages of 18 - 65.

Given these a-priori assumptions, we assumed different baseline vaccination rates of 35%, 50% and 60%, and then computed the sample size needed to detect an increase in vaccination rate of 2%, 3% and 4% respectively. Sample size for the difference in proportion is determined by (Zhong, 2009):

$$N = \frac{1}{2} \left(\frac{z_{\alpha/2} + z_{\beta}}{arcsin\sqrt{p} - arcsin\sqrt{p_0}} \right)^2$$

Where:

 $Z_{\alpha/2}$ and Z_{β} refer to the z critical values for a type I and II error of 0.05 and 0.2 respectively, p_0 and p are the baseline proportion and the new hypothesized proportion respectively, and N is the total sample size, assuming a 1:1 ratio of intervention to control

Baseline vaccination rate	Hypothesize d vaccination rate	Hypothesize d effect size	Hypothesize d Cohen's h	Sample size
35.0%	37.0%	2.0%	4.2%	18080
50.0%	52.0%	2.0%	4.0%	19610
60.0%	62.0%	2.0%	4.1%	18668
35.0%	38.0%	3.0%	6.2%	8080
50.0%	53.0%	3.0%	6.0%	8710
60.0%	63.0%	3.0%	6.2%	8256
35.0%	39.0%	4.0%	8.3%	4570
50.0%	54.0%	4.0%	8.0%	4894
60.0%	64.0%	4.0%	8.2%	4618

In the above table, for each baseline rate and hypothesized rate increase (and associated Cohen's h), we show the estimated total sample size needed for each assumption of baseline vaccination rate and effect size. We note that within each hypothesized effect size, changing assumptions about baseline vaccination rates do not substantially alter the sample size.

Based on this, we believe that a 3% effect size is a reasonable assumption and that a sample size of approximately 8,000 participants will be needed to detect this difference with a type I error rate of 0.05 and a presumed power of 0.80. A participation drop-off of 67% has been observed for digital interventions for increasing influenza vaccination in people with diabetes (i.e., Samson et al., 2020). A recent internal survey of individuals with cardiovascular disease demonstrated a survey completion rate of approximately 7%, indicating that this population may have lower than expected engagement. Based on these calculations, we plan to recruit approximately 49,000 participants, anticipating that on average, engagement may be approximately 16%. A targeted enrollment list of approximately 49,000 individuals with 16% survey completion would reach the estimated analysis population of 8,000 participants needed.

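### The SAP's 8,000 analysed participants fall below every 3-point row of its own sample-size table, so the stated 80% power is about 77% to 80%

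*SAP*

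**What the plan says.** SAP Section 4 sizes the primary comparison with an arcsine formula, type I error 0.05, power 0.80 and 1:1 allocation, and states that "N is the total sample size, assuming a 1:1 ratio of intervention to control". Of the table it says "we show the estimated total sample size needed for each assumption of baseline vaccination rate and effect size". For a 3-point increase the rows read 8,080 (35% to 38%), 8,710 (50% to 53%) and 8,256 (60% to 63%).

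For context it notes that "CDC reported vaccination rates are 47.9% for adults between the ages of 18 - 65" and that studies of messaging and reminders "show a range of effect sizes from 2.5 - 3.5" percentage points.

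It then draws its conclusion from the table, choosing 3 points and stating that "approximately 8,000 participants will be needed to detect this difference with a type I error rate of 0.05 and a presumed power of 0.80". Recruitment follows from that: "we plan to recruit approximately 49,000 participants, anticipating that on average, engagement may be approximately 16" per cent, which "would reach the estimated analysis population of 8,000 participants needed". Two engagement benchmarks are given. One is that "A participation drop-off of 67% has been observed for digital interventions for increasing influenza vaccination in people with diabetes"; the other is an internal survey with about 7% completion.

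Protocol 8.1 has the same formula, definition of N and table, and the same figure of about 8,000. Its recruitment range is 24,000 to 35,000 at 67% to 75% drop-off, and it settles on 35,000.

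**The concern.** The conclusion claims to rest on the table, yet no 3-point row supports 8,000. It lies below the smallest of the three rows, not between them. The remark in Section 4 that the baseline rate makes little difference could justify picking one row or a middle value, but not a number below all of them.

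The figure matters because the SAP treats it as the required analysis population and derives the 49,000 list from it. SAP 8.2 restricts the primary analysis to people who answer the 3-month or 6-month survey, so the number of responders sets the power. If that target is too low, the trial's main stated operating characteristic is too favourable, and a null result would be read against a detectable difference smaller than the true one.

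**Working it through.** **Inputs** (SAP Section 4; two-sided testing confirmed in SAP 8.1): z for two-sided 0.05 = 1.95996; z for 80% power = 0.84162; sum 2.80158; 1:1 allocation; baselines p0 of 35%, 50% and 60%; p = p0 + 3 points.

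**Step 1: reproduce the table.** Let h = 2(arcsin√p − arcsin√p0). The printed formula is ½ × (2.80158 / (h/2))².

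| p0 to p | h | Printed formula | Doubled | Table |
|---|---|---|---|---|
| 35% to 38% | 0.06233 | 4,041.0 | 8,082.0 | 8,080 |
| 50% to 53% | 0.06004 | 4,355.3 | 8,710.5 | 8,710 |
| 60% to 63% | 0.06166 | 4,128.3 | 8,256.6 | 8,256 |

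All nine rows reproduce to within 2 participants, but only after doubling. The formula therefore gives N per arm and the table shows 2N. The table is right; the definition of N as the total is not.

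**Step 2: compare 8,000 with the rows.**
- 35%: 8,080 − 8,000 = 80 short (1.0% of the row)
- 50%: 8,710 − 8,000 = 710 short (8.2%)
- 60%: 8,256 − 8,000 = 256 short (3.1%)

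At exactly 47.9% the same method requires 8,717. Neither a one-sided test (6,366 / 6,861 / 6,504) nor a continuity correction (8,216 / 8,844 / 8,392) produces 8,000.

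**Step 3: power at a given total N.** Power = Φ(h√(N/4) − 1.96). For 50% to 53% at 8,000: 0.06004 × √2,000 = 2.685; 2.685 − 1.960 = 0.725; Φ(0.725) = 76.6%.

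| Total analysed | 35% | 47.9% | 50% | 60% |
|---|---|---|---|---|
| 8,000 | 79.6% | 76.5% | 76.6% | 78.7% |
| 7,840 (16% of 49,000) | 78.8% | 75.7% | 75.7% | 77.9% |

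The pooled-variance formula agrees to within 0.02 percentage points. Solving instead for the increase detected with 80% power at baselines of 35% / 50% / 60% gives 3.02 / 3.13 / 3.05 points at 8,000 and 3.05 / 3.16 / 3.08 points at 7,840.

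**Step 4: completion needed from 49,000.** 8,080 / 49,000 = 16.5%; 8,710 / 49,000 = 17.8%; 8,256 / 49,000 = 16.8%.

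**Step 5: Protocol 8.1.** The low end, 24,000 × 0.33 = 7,920, is below all three rows (power 79.2% / 76.2% / 78.3%). The chosen 35,000 × 0.25 = 8,750 covers all three (83.0% / 80.2% / 82.2%).

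**Step 6: scale against other uncertainties.** At 8,000 and a 50% baseline, the cited effect range gives 61% power at 2.5 points and 88% at 3.5. For 50% to 53% from 49,000, power by completion rate is 42% at 7% (3,430), 76% at 16% (7,840), 84% at 20% (9,800) and 97% at 33% (16,170). The 33% is the complement of the 67% drop-off.

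**The case against.** The SAP says approximately and calls the power presumed, and the full table stands just above the sentence. At 35% and 60% the cost is only 0.4 and 1.3 power points. The SAP never names 50% or 47.9% as its planning baseline; SAP Section 1 gives 47.9% for high-risk people aged 18 to 64, while the trial has no upper age limit. The cited completion rate and effect range move power far more. In the Protocol, the chosen 35,000 already covers the largest row (8,710 / 0.25 = 34,840), so the understated figure there changed no decision. Finally, these powers are for an unadjusted comparison, whereas SAP 8.5 also plans a covariate-adjusted logistic model.

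Much of this stands. The 35% gap is rounding, as is 7,840 against 8,000. The 7% rate is a stress case: it comes from one internal survey, and applying it to people who answer either of two surveys is an assumption. A completion-rate line and a rewritten Protocol range are optional, and the restated power should be labelled unadjusted.

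What does not stand is that approximately covers the conclusion. It does not cover 710 participants and 3.4 power points at 50%, and the figure is below every row, so no choice of tabulated baseline supports it.

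**Conclusion.** The concern holds: the stated 80% power at 8,000 is wrong as written, by the plan's own table. The overstatement is 0.4, 3.4 and 1.3 percentage points at baselines of 35%, 50% and 60%. The planned yield of about 16% of 49,000 meets none of the 3-point rows. The labelling of N is a separate slip in both documents and leaves the table values intact.

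The consequence is modest. It does not bias the estimate or affect type I error; it affects only what the plan says it can detect. These results assume the SAP's own inputs: an unadjusted two-sided comparison at 0.05, 1:1 among those analysed, and a 3-point absolute increase. Covariate adjustment could shift the power slightly. The 16% lies between the two cited benchmarks, but its derivation is not shown. It should be corrected, though it is not critical.

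**What to change.** **SAP Section 4.** Replace the 8,000 and 0.80 statement with text such as: *The table requires 8,080 to 8,710 analysed participants for 80% power, depending on baseline. About 7,840 to 8,000 responders (about 16% of 49,000) give about 76% to 80% unadjusted power for a 3-point increase across the tabulated baselines, or 80% power for an increase of about 3.0 to 3.2 points.* Define N in the formula as the number per arm and note that the table shows 2N.

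**Optional in the SAP.** Add one line of power for 50% to 53% by completion rate (figures above), with 7% marked as a stress case and a note that 16% lies between the two cited benchmarks.

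**Protocol 8.1.** Give the requirement as 8,080 to 8,710 and correct the definition of N. If the recruitment range is also revised, its lower figure becomes about 24,500 to 26,400 (8,080 / 0.33 = 24,485; 8,710 / 0.33 = 26,394); the 35,000 stands. If the Protocol is not to be amended, record these corrections in SAP Section 6, which lists modifications to the Protocol's statistical section.

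**Cost.** Text only: no added enrolment and no change to any analysis. The stated power becomes slightly less favourable. Editing the Protocol needs IRB review under its Statement of Compliance; recording the correction in SAP Section 6 leaves the Protocol text unchanged.

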8 STATISTICAL METHODS

8.1 General Statistical Approaches

For the study variables, we will perform distributional analysis. When describing the study population, we will use min, max, mean, and standard deviations for continuous variables (i.e. age, BMI) and frequency counts for categorical variables (i.e. gender, ethnicity). For both continuous and categorical variables, we will report on the number of participants evaluated for that variable, as well as the number of people with non-missing values. For the study variables, we will also look at individual-level rates of missing data. Missing data or unknown responses will be described separately and not be counted in the summary descriptions of the variables. We will report on the percent of missing data for each of the included data sources (surveys, activity data) and evaluate whether any missingness is associated with baseline participant-level characteristics in the case of missing survey data or with the outcome in the case of activity tracker data.

Statistical testing comparing variables will be performed at the 5% significance level using two-sided tests or two-sided 95% confidence intervals (CI), unless otherwise specified. Comparison of means will use Student's t-test for normal distributions, or a Mann-Whitney U test for non-normal distributions. Comparisons of frequencies will use chi-square tests. Regression modeling approaches are described below. We will report on the size of the beta-parameter estimate and the associated significance level (p-value) for each predictor variable.

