8.2 Analysis Population (s)

The analysis populations will consist of:

- P1: This population will consist of all individuals who respond to the 3-month or 6-month survey. It will
 be used for the primary objective analysis and for the first part of the secondary objective (examine
 predictors of vaccination status across the CVD-I and CVD-C arms). This population will also be used
 for the second exploratory objective, which is to describe self-reported complications from influenza
 during the study period.
- P2: This population will consist of all individuals who are in the CVD-I arm and have responded to the 3-month or 6-month survey. It will be used for the second part of the secondary objective, which is to describe the engagement with different intervention messages and its relationship to influenza vaccination status.
- P3a: This population will consist of individuals who responded to the baseline, 3-month or 6-month survey. It will be used to examine the first part of the exploratory objectives - specifically the selfreported impact of COVID-19 on influenza vaccination and behavior.
- P3b: This population will consist of all individuals who complete either the 3-month or the 6-month survey, who have wearable activity data and who consent in the final (6-month) survey to have the activity data analyzed for this study. This population will be used for the 3rd exploratory objective, specifically to explore the differences in wearable data (i.e., sleep, steps, heart rate) between individuals who experience influenza and those who do not, as well as differences in wearable data between cardiovascular conditions.

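### The 49,000 target rests on an unsourced 16% completion rate, while the SAP's only figure for people with cardiovascular disease is about 7%, and no rate from 7% to 16% gives the stated 0.80 power

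*SAP*

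**What the plan says.** SAP section 4 (Sample Size) settles on a 3-point increase ("we believe that a 3% effect size is a reasonable assumption") and about 8,000 analysed participants, "with a type I error rate of 0.05 and a presumed power of 0.80". It then gives two observed response figures. One is a 67% drop-off, that is 33% completion, in a digital vaccination trial in people with diabetes. The other is closer to the trial population: "A recent internal survey of individuals with cardiovascular disease demonstrated a survey completion rate of approximately 7" per cent. The SAP itself takes this as a sign that engagement may be lower than expected. It continues: "we plan to recruit approximately 49,000 participants, anticipating that on average, engagement may be approximately 16" per cent, and says that a list of that size at that completion rate would supply the 8,000.

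The protocol (section 8.1) had planned about 35,000 on a 67% to 75% drop-off.

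SAP section 8.2 defines P1, the population for the primary analysis: "This population will consist of all individuals who respond to the 3-month or 6-month survey". A person who answers only the baseline survey is not in P1.

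**The concern.** Everyone eligible has self-reported a cardiovascular condition (SAP section 5), so the cardiovascular completion figure is the more relevant of the two cited. The planning rate is more than twice that figure, and section 4 shows no calculation that leads to it. The midpoint of 7% and 33% is 20%, not 16%. The midpoint of 7% and the protocol's 25% (75% drop-off) is 16%, but neither document says the rate was obtained that way.

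The list size and the power statement both depend on this one rate. If completion is nearer the cardiovascular figure, the primary comparison has clearly less than 0.80 power for the 3-point target, and section 4 does not show by how much.

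**Working it through.** **Inputs.** From SAP section 4: list 49,000; planned completion 16%; cardiovascular completion 7%; target increase 3 points; power 0.80; baselines as in "we assumed different baseline vaccination rates of 35%, 50% and 60" per cent; allocation "assuming a 1:1 ratio of intervention to control". From SAP section 8.1: tests "performed at the 5% significance level using two-sided tests". From SAP section 8.2: P1 is response to the 3-month or the 6-month survey. Assumption not in the documents: 7% applies to each follow-up survey. No overlap figure is given, so the full range is shown.

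**Step 1. The plan's own figures.** 49,000 × 0.16 = 7,840, and 8,000 / 0.16 = 50,000. Both agree with the stated pair to within about 2%. The table totals also reproduce. For 50% to 53%, arcsin√0.53 − arcsin√0.50 = 0.03002, so ½ × (2.802 / 0.03002)² ≈ 4,355 per arm, or 8,711 in total against the tabled 8,710. (The printed formula gives the per-arm number although it is labelled as the total. The tabled totals are right, so this does not matter here.)

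**Step 2. Share of the list entering P1 if each follow-up survey is answered by 7%.**

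- Same people answer both: 7%; 49,000 × 0.07 = 3,430.
- Independent responses: 1 − 0.93² = 13.5%; about 6,620.
- No overlap: 7% + 7% = 14%; 49,000 × 0.14 = 6,860.

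So 7% per survey cannot add up to 16% over the two surveys that define P1. Adding a third 7% from baseline would give 21% (10,290), but P1 does not count baseline-only responders.

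**Step 3. Power for a 3-point increase.** With n = N/2 per arm and p̄ the mean of p₀ and p₁:

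power = Φ[(0.03 − 1.96 × SE₀) / SE₁], SE₀ = √(2p̄(1 − p̄)/n), SE₁ = √((p₀(1 − p₀) + p₁(1 − p₁))/n).

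Example: N = 3,430, n = 1,715, 50% to 53%. SE₀ = 0.01707, SE₁ = 0.01706, (0.03 − 0.0335)/0.01706 ≈ −0.20, power 0.42.

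**Step 4. Detectable difference.** This is the increase at which the same formula gives 0.80.

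| Share in P1 | N | Power at baseline 35% / 50% / 60% | Difference detectable with 0.80 power |
|---|---|---|---|
| 7% (full overlap) | 3,430 | 0.45 / 0.42 / 0.44 | 4.6-4.8 points |
| 13.5% (independent) | 6,620 | 0.72 / 0.69 / 0.71 | 3.3-3.4 points |
| 14% (no overlap) | 6,860 | 0.73 / 0.70 / 0.72 | 3.3-3.4 points |
| 16% (SAP) | 7,840 | 0.79 / 0.76 / 0.78 | 3.1-3.2 points |

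The small shortfall at 16% arises because 7,840 is below all three tabled totals for a 3-point effect (8,080, 8,710 and 8,256). The larger shortfalls come from the completion rate.

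**The case against.** The best defence is that section 4 is open about the uncertainty. It discloses the 7%, says engagement may be low, raises the list from the protocol's 35,000 to 49,000, and picks a rate between a high and a low figure in hedged language. Its statement about reaching 8,000 is conditional on 16% completion. All of that stands, and it rules out two stronger readings. A reader might infer an arithmetic error, but the multiplication is sound once 16% is granted. A reader might also take the 8,000 as an unconditional promise, which the text does not make.

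Nor do the documents support a forecast that P1 will be 3,430 to 6,860. The internal survey is described only as one of people with cardiovascular disease. Its match to the trial's criteria and its length, reminders and incentives are not given. The trial allows reminders by email, text and push notification (SAP section 5, Study Compliance) and pays 300 points per survey (Protocol section 6.5). Completion could therefore exceed 7% per survey, and 14% is a ceiling only if the 7% carries over unchanged.

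Finally, it is tempting to say the trial could detect only effects at or above the top of the cited 2.5-3.5 point range. That confuses the difference with 0.80 power and the smallest significant one. At a 50% baseline, an observed difference of about 1.96 × 0.01707 = 3.3 points would be significant at N = 3,430, and about 2.4 points at N = 6,860. A low-powered null result could be misread, but this is secondary: SAP section 8.5 already plans 95% confidence intervals for the odds ratios, and section 8.3 reports response by arm and survey.

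What the defence does not supply is a basis for 16%, or any statement of power at a lower yield.

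**Conclusion.** The point holds as an unsupported planning assumption. The 16% has no stated source, and it is more than double the only completion figure the SAP gives for people with cardiovascular disease. Between 7% and 16%, expected P1 runs from 3,430 to 7,840 and power for a 3-point increase from about 0.42 to 0.79, so the stated 0.80 is not reached anywhere in that range. At the upper end the gap is small; at the lower end it is large.

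The power figures rest on a normal approximation for two proportions, equal arms among responders, and the SAP's own baselines. The 3,430-6,860 range also assumes 7% at each follow-up survey, which the documents neither confirm nor exclude.

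**What to change.** In SAP section 4:

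- Label 16% as an assumption about the proportion answering at least one of the 3-month and 6-month surveys, or give its basis in those terms.
- Replace the single statement of 8,000 participants and 0.80 power with expected P1, power for 3 points, and the difference detectable with 0.80 power, over 7% to 16%. The rows would be: 3,430, about 0.42-0.45, 4.6-4.8 points; 6,860, about 0.70-0.73, 3.3-3.4 points; 7,840, about 0.76-0.79, 3.1-3.2 points.
- State that the first two rows assume 7% per follow-up survey, with full overlap and with none.

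The cost is a change of wording and a less favourable stated power. Enrolment, endpoint, analysis population and model stay as they are.
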